7. DATA HANDLING

7.1. Methods for Handling Missing Dates

All analyses and descriptive summaries will be based on the observed data. Except for the data otherwise specified in the language below, missing data will not be imputed or “carried forward”. For the subject data listings, no imputation of incomplete dates will be applied. The listings will present the incomplete dates without any change.

Missing or Partial Death Dates

- If the entire date is missing, the death date will be imputed as the day after the date of last contact.
- If the day or both day and month is missing, the death date will be imputed to the maximum of the full (non-imputed) day after the date of last contact and the following:
 - If day is missing, day will be 1st of the month
 - If both day and month are missing, death month and day will be January 1st.

Date of Last Dose of All Study Drugs

No imputation will be done for first dose date. Date of last dose of study drug, if unknown or partially unknown, will be imputed as follows:

- If the last date of study drug is completely missing and the End of Treatment eCRF page has not been completed and no death date has been entered, the patient should be considered ongoing and the cutoff date for the analysis should be used as the last dosing date.

- If the last date of study drug is completely or partially missing and there is EITHER a completed End of Treatment eCRF page OR a death date available (within the data cutoff date), then impute this date as the last dose date:
 - = 31DECYYYY, if only Year is available and Year < Year of min (EOT date, death date)
 - = Last day of the month, if both Year and Month are available and Year = Year of min (EOT date, death date) and Month < Month of min (EOT date, death date)
 - = min (EOT date, death date), for all other cases.

Missing Dates in Adverse Events/Concomitant Therapies

Dates missing the day or both the day and month of the year will adhere to the following conventions:

- The missing day of onset of an AE or start date of a therapy will be set to:
 - first day of the month that the event occurred, if the onset yyyy-mm is after the yyyy-mm of first study treatment
 - the day of the first study treatment, if the onset yyyy-mm is the same as yyyy-mm of the first study treatment
 - the date of informed consent, if the onset yyyy-mm is before the yyyy-mm of the first treatment
- The missing day of resolution of an AE or end date of a therapy will be set to:

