 - the last day of the month of the occurrence. If the subject died in the same month, then set the imputed date as the death date
- If the onset date of an AE or start date of a therapy is missing both the day and month, the onset date will be set to:
 - January 1 of the year of onset, if the onset year is after the year of the first study treatment
 - the date of the first treatment, if the onset year is the same as the year of the first study treatment
 - the date of informed consent, if the onset year is before the year of the first treatment
- If the resolution date of an AE or end date of a therapy is missing both the day and month, the date will be set to:
 - December 31 of the year of occurrence. If the subject died in the same year, then set the imputed date as the death date

- If date is completely missing, then no imputation will be done and the event will be considered as treatment emergent (for AEs) or concomitant (for medications) unless the end date rules out the possibility.

Missing Efficacy Endpoints

For primary and secondary efficacy analyses no values will be imputed for missing data. For time to event endpoints, non-event observations will be censored and for ORR/DCR, patients with no post-baseline tumor evaluations or missing baseline tumor evaluation will be counted as non-responders.

Missing Age

If age is missing, age will be computed from birth date to the date of Informed Consent, as $(\text{Date of Informed Consent} - \text{Date of Birth} + 1) / 365.25$ round down to the nearest integer.

- If birth date is missing day, day will be set to 15th to minimize bias
- If missing both month and day, birth date will be set to July 1 of the birth year

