
PR: Two objective statuses of PR or better (PR followed by PR or PR followed by CR) a minimum of four weeks apart documented before progression and start of new anti-cancer therapy, but not qualifying as CR. Sequences of PR- SD- PR are considered PRs as long as the two PR responses are observed at a minimum of 4 weeks apart.

SD: At least one objective status of stable or better documented at least 8 weeks after start date and before progression and the start of new anti-cancer therapy but not qualifying as CR or PR.

PD: Progression documented within 16 weeks after start date and not qualifying as CR, PR or SD.

Not Evaluable (NE): All other cases. Note that reasons for NE should be summarized and the following reasons could be used:

- Early death (Note: death prior to 8 weeks after start date)
- No post-baseline assessments
- All post-baseline assessments have overall response NE
- New anti-cancer therapy started before first post-baseline assessment
- SD too early (<8 weeks after start date)
- PD too late (>16 weeks after start date)

Special and rare cases where BOR is NE due to both early SD and late PD will be classified as 'SD too early'.

Derivation of BOR

The following table provides the derivation of BOR.

Table 3 Derivation of Best Overall Response when confirmation of response is required

Objective status at:

Assessment 1	Assessment 2	Assessment 3	Assessment 4	Overall Response
Death				NE
CR	CR	PD		CR
CR	NE	CR	PD	CR
PR	CR	CR	PD	CR
PR	CR	PD		PR
PR	PR	PD		PR
PR	SD or NE	PR	PD	PR
PR	PR	CR	PD	PR
CR	PR			Not allowed. Reappearance is progression
CR	PD or No or NE			SD
PR	PD or No or NE			SD
SD or NE	CR	PD		SD
SD or NE	PR	PD		SD
SD	PD			SD
PD				PD
No or NE assessment				NE
NE	PD			PD
NE	No or NE assessment			NE
NE	NE	PD		NE

Objective response rate (ORR) is defined as the proportion of patients with a documented complete response (CR) or partial response (PR) based on RANO criteria as determined by the investigator assessment collected in the CRFs, relative to the Full Analysis Set.

The DCR is the proportion of patients whose best overall response is CR, PR or SD based on RANO full analysis set. The best response of SD can be assigned if SD criteria were met at least once after first dose date at a minimum interval of 8 weeks from BBI608. New anti-cancer treatment will be derived based on Concomitant Medication if available.

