10.2. Appendix 1.2 Censoring for Time to Event Data

Table 4 summarizes the censoring rules for the PFS analysis and displays censoring hierarchy for this study. Table 5 shows the general reasons for PFS censoring and where the censoring hierarchy in **Table 4** came from.

Table 4 Event or Censor Time for PFS and Censoring Hierarchy

Censoring Hierarchy	Situation	Date of Event or Censor	Event / Censor
1	No baseline radiological tumor assessment available	Date of First Dose	Censored
2	New anticancer treatment started and no tumor progression	Date of previous adequate radiological assessment immediately prior to start of new therapy or Date of first dose, whichever comes later	Censored
3	Tumor progression (per RANO) documented after 2 scan intervals following previous adequate radiological tumor assessment	Date of previous adequate radiological assessment or Date of first dose, whichever comes later	Censored
4, 5	No tumor progression (per RANO) and subject lost to follow-up or withdrawal of consent	Date of last adequate radiological Assessment or Date of first dose, whichever comes later	Censored
6	No post baseline radiological tumor assessment available and no death reported within 2 scan intervals following the date of the first dose of study drug (BBI608)	Date of First Dose	Censored
7	No post baseline radiological tumor assessment available but death reported within 2 scan intervals following the date of the first dose of study drug (BBI608)	Date of Death	Event

	No tumor progression (per RANO) and no death reported within 2 scan intervals following last adequate radiological tumor assessment	Date of last adequate radiological tumor assessment or Date of first dose, whichever comes later	Censored
	No tumor progression (per RANO) but death reported within 2 scan intervals following last adequate radiological tumor assessment	Date of death	Event
	Tumor progression (per RANO) documented within 2 scan intervals following previous adequate radiological tumor assessment	Earliest of the target, non-target and new tumor assessment dates	Event

Notes: (1) Symptomatic deteriorations (i.e. symptomatic progressions, which are not radiographically confirmed) will not be considered as progressions.

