(2) If target, non-target and new lesion assessments have different dates within a visit, then the earliest of those dates will be considered as the date of the tumor assessment if the assessment for that visit is progressive disease (PD); otherwise the latest date will be used.

(3) Adequate radiographical tumor assessment refers to an assessment with overall response of CR, PR, SD or PD.

(4) Comparing date of last tumor assessment to date of first dose is necessary if the last tumor assessment is baseline assessment

Table 5 PFS Censoring Reasons and Hierarchy

Hierarchy	Condition	Censoring Reason
1	No adequate baseline assessment	No adequate baseline assessment
2	Start of new anti-cancer therapy before event.	Start of new anti-cancer therapy
3	Event more than 2 weeks from last adequate post-baseline tumor assessment/start date	Event after missing assessments ^a
4	No event and [withdrawal of consent date \geq start date OR End of study (EOS) = Subject refused further FU]	Withdrawal of consent
5	No event and lost to follow-up in any disposition page	Lost to follow-up

6	No event and [EOS present OR disposition page for any EPOCH after screening says patient will not continue into any subsequent phase of the study] and no adequate post-baseline tumor assessment	No adequate post-baseline tumor assessment
7	No event and none of the conditions in the prior hierarchy are met	Ongoing without an event

For OS, patients last known to be alive are censored at date of last contact.

Date of Last Contact

The date of last contact will be derived for patients not known to have died at the analysis data cutoff date using the latest complete date (non-imputed) among the following:

- All patient assessment dates (e.g., blood draws [laboratory, PK], vital signs, performance status, ECG, tumor assessments, concomitant radiation, surgery)
- Start and end dates of follow-up anti-cancer therapies
- AE start and end dates
- Last date of contact where “Subject Remains in Follow-up” collected on the “Survival Follow-up” eCRF (do not use date of survival follow-up assessment unless status is alive)
- Study drug start and end dates
- Date of discontinuation on disposition eCRF pages (do not use if reason for discontinuation is lost to follow-up or death).

Note:

1. This list is not all inclusive and should be agreed upon by the study team according to the data collected in the CRF

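### Partial start dates of new anti-cancer therapy are imputed to the earliest possible date, which can wrongly censor PFS or discard response scans; Tables 4 and 5 disagree on whether a documented progression is lost

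*SAP*

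**What the plan says.** SAP 7.1, under adverse events and concomitant therapies, completes a partial therapy start date as follows (cases on or after first dose):

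- Day missing, later month than first dose: "first day of the month that the event occurred, if the onset yyyy-mm is after the yyyy-mm of first study treatment".
- Day missing, same month as first dose: "the day of the first study treatment, if the onset yyyy-mm is the same as yyyy-mm of the first study treatment".
- Day and month missing, later year: "January 1 of the year of onset, if the onset year is after the year of the first study treatment".
- Day and month missing, same year: "the date of the first treatment, if the onset year is the same as the year of the first study treatment".

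SAP 10.1, in the paragraphs on ORR and DCR, adds: "New anti-cancer treatment will be derived based on Concomitant Medication if available". The documents give no other derivation of this variable.

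SAP 10.2 then uses the start of new therapy for PFS, with different wording in its two tables. Table 5 row 2 censors for "Start of new anti-cancer therapy before event". Table 4 row 2 describes the situation as "New anticancer treatment started and no tumor progression" and dates the censoring at the last adequate scan before the new therapy, or at first dose if that is later. In SAP 10.1, the start of new therapy also ends the period in which CR, PR or SD can be documented.

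Another paragraph of SAP 7.1, on missing efficacy endpoints, says: "For primary and secondary efficacy analyses no values will be imputed for missing data".

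**The concern.** Taking the earliest possible start is cautious for adverse events, because it makes an event more likely to count as treatment-emergent. For new anti-cancer therapy it is not cautious, because the order of therapy start, progression and scans decides the outcome. Subsequent therapy often follows progression. If both fall in one calendar month and the day of the therapy is missing, the rule puts the therapy before the progression that preceded it.

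Nothing in the SAP stops an imputed start from falling before a documented progression or an adequate scan. At stake are the Phase II primary endpoint, PFS-6, in arms with no control group, and also ORR and DCR.

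**Working it through.** **The plan's own figure.** SAP 4.2.2 and Protocol 10.2 state that with 30 patients and a projected PFS-6 of 20%, the lower bound of the exact two-sided 80% interval exceeds 10%. For 6/30 the Clopper-Pearson limits are the 10% quantile of Beta(6, 25) and the 90% quantile of Beta(7, 24), which are 10.86% and 32.47%. The figure reproduces and is not in dispute.

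**One patient with progression (dates assumed).** First dose 16 Jan 2017; stable scan 13 Mar; RANO progression 8 May; new therapy truly started 22 May. PFS in months is (date − first dose + 1)/30.4375, from SAP 8.2.2.2.

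- True start date: event at 113/30.4375 = 3.71 months.
- Recorded as May 2017: imputed to 1 May, before the progression. Table 5 row 2 censors, and Table 4 dates the censoring at 13 Mar: 57/30.4375 = 1.87 months.
- Recorded as 2017: imputed to first dose. Censored on Day 1: 1/30.4375 = 0.03 months.
- Table 4 row 2 read literally: the patient has progressed, so the row does not apply and the event at 3.71 months stands.

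**The same dates without progression.** Suppose the 8 May scan shows stable disease. The correct censoring date is 8 May. The imputed start of 1 May moves it to 13 Mar, and a year-only start moves it to Day 1. Table 4 row 2 applies here on its plain wording, so aligning the tables does not cure this.

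**Best response.** Suppose PR is seen on 13 Mar and again on 8 May. With therapy imputed to 1 May, the second scan no longer precedes new therapy, so the PR is unconfirmed and becomes SD. With a year-only start, no post-baseline scan precedes the therapy, so the patient is not evaluable and counts against both ORR and DCR.

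**How often the order reverses, given a missing day.** Progression, on any day but the 1st, and the therapy start must share a calendar month. Over all 2017 progression dates, for assumed lags of 3, 7, 14, 21 and 28 days, this holds in 87%, 74%, 51%, 28% and 5% of cases.

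**Effect on PFS-6.** Take an assumed arm of 30 with progression at weeks 8, 16 and 24 in 12, 8 and 4 patients, and 6 event-free past 6 months. The Kaplan-Meier estimate is (18/30)(10/18)(6/10) = 20.0%, with 80% log-log interval 11.6% to 30.0%.

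- One early progression censored on Day 1: 6/29 = 20.7%. Three: 6/27 = 22.2%.
- One progression censored at the previous scan: 6/29 = 20.7% if it was at week 8; (18/30)(10/17)(6/10) = 21.2% at week 16; (18/30)(10/18)(6/9) = 22.2% at week 24.
- One at each of the three scans, censored at the previous scan: (18/29)(10/17)(6/9) = 24.3% (80% interval 14.5% to 35.5%).
- One patient who progresses after month 6, censored on Day 1 through a year-only start in the first-dose year: 5/29 = 17.2%.

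Censoring a patient without progression too early also lowers the curve if events follow, because each later factor 1 − d/r then has a smaller r.

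**The case against.** **Table 4 may govern.** SAP 10.2 presents Table 4 as the summary of the censoring rules and Table 5 as the general reasons. A reader might infer from Table 5 that the plan settles the matter and turns documented progressions into censorings. It does not: Table 4 row 2 read literally keeps them as events. This stands, and it limits the progression part of the point to a conflict between the tables. It does not help the patient without progression or the response endpoints.

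**Table 5 row 3.** This row, also read literally, censors any event more than 2 weeks after the last adequate assessment, where Table 4 allows two scan intervals. On that reading the 8 May progression would be censored at 13 Mar even with a complete therapy date. The day-missing example therefore assumes that Table 4's interval is the intended one.

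**No imputation for efficacy.** The sentence in SAP 7.1 could be read to exclude these dates. It is not tied to therapy dates, though. The section's opening excepts whatever it goes on to specify, and it imputes death dates, which feed PFS and OS. Where the authors wanted only non-imputed dates, as for last contact in SAP 10.2, they said so. If the sentence did apply, a partial date could not be ordered against a scan, and the SAP gives no alternative rule. The reach of the imputation is ambiguous.

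**Data source.** The derivation from Concomitant Medication sits in the response text, and Protocol 5.6 collects subsequent therapy separately in follow-up. The link to PFS is an inference from the absence of any other derivation.

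**Size and frequency.** Protocol 5.6 plans monthly follow-up for the first 3 months, which makes year-only dates less likely. A shift of 1 to 2 points is small against an interval of about 11% to 32% in a study with no hypothesis test. Both points are fair.

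**Conclusion.** The point holds as a defect in the date rule together with a conflict between two tables. Under Table 5 row 2, a documented progression can become a censoring at the previous scan or on Day 1; under Table 4 row 2 read literally it cannot. Under either table, an imputed start can move back the censoring date of a patient without progression and remove valid scans from best overall response, ORR and DCR.

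A reader might infer that the error always raises PFS-6. The documents do not support that. Re-dated progressions before 6 months raise it (20.0% to 20.7% for one and 22.2% for three, if censored on Day 1). A late progressor censored on Day 1 lowers it (17.2%), as can early censoring of patients without progression.

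The figures rest on an assumed arm at the projected 20%. The number of partial dates and the lag from progression to therapy are not in the documents. The effect on ORR and DCR is not quantified.

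**What to change.** Add one paragraph to SAP 7.1 and amend one table row:

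1. Exempt anti-cancer therapies from the 7.1 start-date rule, whichever record they come from.
2. State that an imputed start may not precede a documented progression or an adequate scan unless the recorded part of the date requires it. For a missing day, for example, use the day after progression when progression falls in that month, and otherwise the last day of the month. Apply the same principle within the year to year-only dates.
3. Cap the imputed date at death or last contact, so that no therapy starts after the patient has died or was last seen.
4. State that this rule overrides, for this date, the sentence on not imputing values in efficacy analyses.
5. Align Table 5 row 2 with Table 4 row 2.
6. List every patient whose new-therapy date was imputed, with the progression and scan dates beside it.

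The cost is one paragraph, one table row, one programming rule and a short listing. There is a small downside: with the day missing, a scan taken after the therapy really began may occasionally count toward response. The listing lets a reader see those cases.

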8.2.4.1. Adverse Events

Overall Summary of AEs

An AE will be regarded as **treatment-emergent**, if

- it occurs for the first time on or after the first dose date of either BBI 608 or TMZ up to 30 days after the last dose of study treatment; or
- it occurs prior to first dose date of either BBI 608 or TMZ and worsens in severity on therapy or up to 30 days after the last dose of study treatment

Last dose of study treatment will be obtained from either drug administration or end of treatment CRF, whichever comes later.

Concurrent conditions from CRF collecting Adverse Event include any event or condition that was active at the time of starting on study. Entries have a start date and a severity grade. This will be considered a baseline AE and be used to derive treatment-emergent AE.

Adverse events will be coded by SOC and PT using the MedDRA[®] version 19.0. The severity of AEs will be graded by the investigator using NCI CTCAE Version 4.0. The verbatim term will be included in the AE listings.

An overview of treatment-emergent adverse events (TEAEs) will be provided. The number and percentage of subjects with following will be summarized for:

1. Subjects with at least one TEAE
2. Subjects with TEAE of CTCAE grade 3 or higher
3. Subjects with serious TEAE
4. Subjects with serious TEAE related to BBI608
5. Subjects with serious TEAE related to TMZ
6. Subjects with BBI 608 related TEAE
7. Subjects with BBI 608 related TEAE of CTCAE grade 3 or higher
8. Subjects with TMZ related TEAE
9. Subjects with TMZ related TEAE of CTCAE grade 3 or higher
10. Subjects with TEAE related to study drug (BBI608 or TMZ)
11. Subjects with study drug (BBI608 or TMZ) related TEAE of CTCAE grade 3 or higher
12. Subjects with TEAEs leading to BBI-608 being held
13. Subjects with TEAE leading to dose reduction BBI-608
14. Subjects with TEAE leading to BBI-608 dose discontinuation
15. Subjects with TEAE leading to TMZ being held
16. Subjects with TEAE leading to dose reduction of TMZ

Summary of AEs by System Organ Class and Preferred Term

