The number and percentage of subjects with TEAEs by SOC and PT and maximum CTCAE grade will be summarized. A summary of TEAEs of CTCAE grade 3 or higher (Grade 3, 4, 5) will be presented by SOC and PT and maximum CTCAE grade. A summary of TEAEs by SOC, PT and maximum grade will be presented in the descending order of frequency counts for all grades. The most commonly reported AEs using different cutoffs (e.g., 2%, 5% or 10% or more of patients in either arm) may also be summarized by PT as needed for various reporting purposes. Adverse events associated with dose held/dose reduction of either BBI608 and/or Temozolomide will also be summarized by SOC and PT and maximum CTCAE grade.

Treatment Related TEAE

AEs reported with a relationship to a treatment considered by the investigator to be 'possible', 'probable' or 'definite' will be considered "Related" to study treatment or combination drug, respectively. AEs reported with a relationship to a treatment considered by the investigator to be "unlikely" or "unrelated" will be considered as "Not Related" to study treatment or TMZ, respectively. Missing relationship will be considered as "Related". Similar summaries of all causality AEs will be provided along with TEAEs leading to dose modification, reduction, or discontinuation.

Serious AE and Death

Treatment emergent SAEs and treatment related SAEs will be summarized by MedDRA SOC and PT and Maximum CTCAE grade.

Patients who experienced a SAE during AE reporting period will be listed for all safety patients. The number and percentage of patients who experience any treatment emergent SAE will be summarized by SOC, PT and maximum CTCAE grade. Similar summary for treatment related TESAE will be provided as well.

Deaths that occur on or after the first dose of study treatment and within 30 days of last dose of any study treatment will be summarized. The number and percentage of subjects who died during the study treatment and within 30 days after the last dose will be presented.

TEAE or TESAEs leading to death will also be summarized by MedDRA, SOC, PT, and Maximum CTCAE grade.

A listing of death data will also be provided and it will include all deaths that occurred during the reporting period for deaths, which starts from the signing of informed consent to the end of the follow up period. The listing will include date of death, and the number of days relative to the administration of first and last dose.

Adverse Events of Clinical Relevance

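### SAP 7.1 checks the AE end date only when the onset date is completely missing, so an event that ended before first dose but has a partial onset date can be counted as treatment-emergent

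*SAP*

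**What the plan says.** SAP 7.1 has three levels of rule for an incomplete AE onset (or therapy start) date.

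- **Day missing.** If the month matches that of first dose, onset becomes "the day of the first study treatment, if the onset yyyy-mm is the same as yyyy-mm of the first study treatment". For an earlier month it becomes "the date of informed consent, if the onset yyyy-mm is before the yyyy-mm of the first treatment".
- **Day and month missing.** If the year matches, onset becomes "the date of the first treatment, if the onset year is the same as the year of the first study treatment". For an earlier year it becomes "the date of informed consent, if the onset year is before the year of the first treatment".
- **Date completely missing.** Nothing is imputed, and "the event will be considered as treatment emergent (for AEs) or concomitant (for medications) unless the end date rules out the possibility".

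Only the third level mentions the end date.

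SAP 8.2.4.1 then defines a treatment-emergent AE (TEAE) by date. An event first occurring from the first dose of either drug until 30 days after the last dose qualifies. An event that began earlier qualifies only if its severity worsens. The same section has a baseline rule: "Concurrent conditions from CRF collecting Adverse Event include any event or condition that was active at the time of starting on study". Such entries carry a start date and a grade, are treated as baseline AEs, and feed into the TEAE derivation. On causality it says "Missing relationship will be considered as" related.

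SAP 7.1 also says that subject listings show incomplete dates as recorded, without imputation.

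**The concern.** The end-date check is attached to the records with the least information and left off those with more. An AE with a known end date before first dose and no onset date is excluded from the TEAE tables. If the site also enters the onset month or year, and it matches first dose, the same AE is included. The imputed onset then falls after the event's own end, which is impossible rather than merely cautious.

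The by-arm TEAE tables are at stake, together with the related-TEAE tables when the relationship field is blank. The study has no control arm in which misdated events would also appear. Because listings keep the raw dates, a listing could show an event that ended before dosing while the summary table counts it as treatment-emergent.

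**Working it through.** No figure in the documents depends on this rule, so there is none to reproduce. The check is to apply the rules as written, and then to see how often they would move a pre-dose onset.

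**Step 1. Can pre-dose AEs be in the data?** Protocol 5.3 lists AE assessment from the date of consent, and Protocol 5.2 allows consent about one month before the first BBI608 dose. Appendices A and B both mark AEs at baseline. Protocol 8.1.1 instead starts AE documentation at enrollment, which Protocol 5.1 and 11.2 define differently. Even so, the second part of the SAP's TEAE definition presupposes records of events that began before dosing.

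**Step 2. Worked cases.** Illustrative dates: consent 1 March 2017, first dose 20 March 2017.

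| Recorded onset | Recorded end | Onset under SAP 7.1 | TEAE by date? |
|---|---|---|---|
| March 2017, day missing | 10 March 2017 | 20 March 2017 | Yes, with onset 10 days after the end |
| 2017 only | 10 March 2017 | 20 March 2017 | Yes, with onset 10 days after the end |
| Completely missing | 10 March 2017 | None imputed | No, the end date rules it out |
| February 2017, day missing | 10 March 2017 | 1 March 2017 (consent) | No |
| 2016 only | Not needed | 1 March 2017 (consent) | No |

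The first three rows could describe one event recorded with different degrees of completeness. Only the completely undated version is classified correctly. With an end-date check on partial dates, the first two rows change to not treatment-emergent.

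**Step 3. How often would a pre-dose onset be moved?** Assumptions: first dose uniform over a 365-day year, and true onset uniform over the W days before it. For an onset L days before dose:

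- Day missing: the onset is in the same month with probability (365 − 12L)/365, for L up to 28. The average L is (W + 1)/2. For W = 10 this gives (365 − 12 × 5.5)/365 = 299/365 = 82%. For W = 28 it gives (365 − 12 × 14.5)/365 = 191/365 = 52%. Direct enumeration for W = 30 gives 49%.
- Day and month missing: the onset is in the same year with probability (365 − L)/365. For W = 10 this averages 359.5/365 = 98.5%; for W = 28, 350.5/365 = 96%; for W = 30, 349.5/365 = 96%.

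These shares apply only to AEs that have a partial onset date and truly began before dosing. An affected AE must also have ended before dosing. That favours longer lags, so for a given W the shares among affected AEs would be somewhat lower. The documents give no count of such records, so the shares cannot be turned into an expected number.

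**Step 4. Size per patient.** SAP 8.2.4 summarizes safety by arm, and up to 30 patients are expected in each. One misclassified patient moves a preferred-term rate by 1/30 = 3.3 percentage points.

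**The case against.** The best defence is that the rule is deliberately conservative. It can only add TEAEs, and sponsors often resolve uncertain timing against the drug. That is sound where timing is uncertain, and such events should remain TEAEs. It does not cover an event whose recorded end precedes first dose, and the SAP accepts this in its own rule for completely missing dates.

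A second defence is that the affected set is narrow: a partial onset in the same month or year as first dose, and resolution before dosing. Earlier months and years go to the consent date and so stay pre-treatment. Counting the event as related needs a second missing field on the same record. All of this stands and limits the importance of the point.

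A reader might infer something stronger: that neurological symptoms already present from the recurrence are turned into TEAEs because baseline status is ignored. The documents do not support that. SAP 8.2.4.1 treats conditions active at study start as baseline AEs and uses them in deriving TEAEs, and imputing a date does not remove a recorded grade. What is missing is the order of the two rules, because the SAP does not say which governs when a concurrent condition's onset is imputed to the first-dose date. An event that resolved before dosing may not count as active at study start, so the baseline rule does not clearly protect it.

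A reader might also infer that the six-patient safety cohorts or the Phase Ib primary endpoint are affected. They are not. The cohorts are judged on DLTs, which are reported as listings (SAP 8.2.2.1), and no cohort-level TEAE table is planned.

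**Conclusion.** The point holds as a narrow defect in a stated rule. Followed exactly, SAP 7.1 can date an AE after its own end and count it as treatment-emergent, when a less complete record of the same AE would be excluded. The order of the partial-date rule and the baseline-AE rule is also unstated.

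The error is a conservative overcount in descriptive by-arm tables, worth 3.3 points per affected patient in an arm of 30. Its frequency is unknown, and the shares in the working rest on the uniform-timing assumptions given there. DLT listings, PFS-6 and the choice of RP2D are unaffected, and the SAP tests no hypothesis. The change is worth making because it is cheap and removes a contradiction between tables and listings, not because it would alter the trial's main conclusions.

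**What to change.** In SAP 7.1, extend the existing condition, "unless the end date rules out the possibility", to partial onset dates:

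- If the end date is before first dose, the AE is not treatment-emergent, and its imputed onset may not be later than that end date. Use the end date as recorded, or its latest possible value if it is partial.
- If the end date is missing, or could fall on or after first dose, keep the present rule. Events of truly unknown timing then remain TEAEs.
- Apply the same check to therapies, so that a medication stopped before first dose is not classed as concomitant because of a partial start date.

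In SAP 8.2.4.1, state that the baseline-AE designation takes precedence over an imputed onset, so that a concurrent condition is a TEAE only if its grade worsens after first dose.

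The cap on onset can always be met. If an event began in the month or year of first dose and ended before first dose, there is at least one pre-dose day in that month or year. The cost is a few lines of SAP text and programming. TEAE counts may fall slightly.
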